9.2.1. Serious Adverse Events

An SAE is any AE from this study that results in one of the following outcomes:

- Death
- Initial or prolonged inpatient hospitalization
- A life-threatening experience (that is, immediate risk of dying)
- Persistent or significant disability/incapacity
- Congenital anomaly/birth defect
- Important medical events that may not be immediately life-threatening or result in death or hospitalization but may jeopardize the patient or may require intervention to prevent one of the other outcomes listed in the definition above. Examples of such medical events include allergic bronchospasm requiring intensive treatment in an

emergency room or at home, blood dyscrasias or convulsions that do not result in inpatient hospitalization, or the development of drug dependency or drug abuse.

- When a condition related to the prefilled pen necessitates medical or surgical intervention to preclude either permanent impairment of a body function or permanent damage to a body structure, the serious outcome of "required intervention" will be assigned.
- Severe hypoglycemia events: episodes of severe hypoglycemia as determined by the investigator according to the definition provided in Sections 9.4.1 and 9.4.2 must be reported as SAEs.

Although all AEs occurring after signing the ICF are recorded in the case report form (CRF), SAE reporting begins after the patient has signed the ICF and has received IP. However, if an SAE occurs after signing the ICF, but prior to receiving IP, it needs to be reported ONLY if it is considered reasonably possibly related to study procedure.

Study site personnel must alert Lilly or its designee of any SAE within 24 hours of investigator awareness of the event via a sponsor-approved method. If alerts are issued via telephone, they are to be immediately followed with official notification on study-specific SAE forms. This 24-hour notification requirement refers to the initial SAE information and all follow-up SAE information. Patients with a serious hepatic adverse event should have additional data collected using the CRF.

Pregnancy (during maternal or paternal exposure to IP) does not meet the definition of an AE. However, to fulfill regulatory requirements, any pregnancy should be reported following the SAE process to collect data on the outcome for both mother and fetus.

Investigators are not obligated to actively seek AEs or SAEs in patients once they have discontinued and/or completed the study (the patient summary CRF has been completed). However, if the investigator learns of any SAE, including a death, at any time after a patient has been discharged from the study, and the investigator considers the event reasonably possibly related to the study treatment or study participation, he/she must promptly notify Lilly.

9.2.1.1. Suspected Unexpected Serious Adverse Reactions

Suspected unexpected serious adverse reactions (SUSARs) are serious events that are not listed in the IB and that the investigator identifies as related to IP or procedure. United States 21 CFR 312.32 and European Union Clinical Trial Directive 2001/20/EC and the associated detailed guidances or national regulatory requirements in participating countries require the reporting of SUSARs. Lilly has procedures that will be followed for the identification, recording, and expedited reporting of SUSARs that are consistent with global regulations and the associated detailed guidances.

9.2.2. Complaint Handling

Lilly collects product complaints on IPs and drug delivery systems used in clinical studies in order to ensure the safety of study participants, monitor quality, and to facilitate process and product improvements.

Patients will be instructed to contact the investigator as soon as possible if he or she has a complaint or problem with the IP and/or drug delivery system so that the situation can be assessed.

- Complaints must be reported by site staff within 24 hours of notification to the clinical site/study personnel, or within 24 hours of study/site personnel becoming aware of a product issue, regardless of the availability of the complaint sample.
- Retain the IP under appropriate storage conditions, if available or when obtained, until instructed to return it to Lilly.
- Product complaints for non-Lilly Products (including concomitant drugs) that do not have a Lilly Product Batch or Control number, are reported directly to the manufacturer per product label.
- Follow the instructions outlined in the Product Complaint Form for other reporting requirements.

9.3. Treatment of Overdose

Excess insulin administration may result in hypoglycemia. Refer to the IB for LY900014 and product label for insulin lispro.

9.4. Safety

9.4.1. Hypoglycemia

Patients are encouraged to perform SMBG, whenever hypoglycemia may be suspected, either by symptoms experienced or perceived increased risk as related to dietary intake, physical activity, or inadvertent or atypical insulin dosing. All patients will be instructed to treat a BG \leq 70 mg/dL (3.9 mmol/L) as hypoglycemia.

Hypoglycemia events will be collected in the patient diaries provided by the sponsor via the investigator. If a hypoglycemia event is suspected, the patient should record the BG value, any associated symptoms, and the treatment administered in the patient diary. The patient should contact the site as necessary. Reports of hypoglycemia will be classified by the investigator as "severe" or "not severe" based upon data collected in the patient diary and in consultation with the patient; see below and Section 9.2.1. All episodes of severe hypoglycemia must be collected as AEs via electronic data entry and reported as SAEs.

Hypoglycemia will be described using the following definitions:

Documented Glucose Alert Level, BG ≤ 70 mg/dL (3.9 mmol/L)

- **Documented symptomatic hypoglycemia:** with typical symptoms of hypoglycemia.
- **Documented asymptomatic hypoglycemia:** without typical symptoms of hypoglycemia.
- **Documented unspecified hypoglycemia**: with no information about symptoms of hypoglycemia available.

Documented Clinically Significant Hypoglycemia with similar criterion as above except for threshold BG <54 mg/dL (3.0 mmol/L)

- Documented symptomatic hypoglycemia
- Documented asymptomatic hypoglycemia
- Documented unspecified hypoglycemia

Severe hypoglycemia

• Severe hypoglycemia (in adults): Patients had altered mental status, and could not assist in their own care, or were semiconscious or unconscious, or experienced coma with or without seizures, and the assistance of another person was to actively administer carbohydrate, glucagon, or other resuscitative actions. Plasma glucose measurements may not be available during such an event, but neurological recovery attributable to the restoration of BG concentration to normal is considered sufficient evidence that the event was induced by a low BG concentration (BG ≤70 mg/dL [3.9 mmol/L]).

Other hypoglycemia:

- **Nocturnal hypoglycemia:** Any documented hypoglycemic event (including severe hypoglycemia) that occurs between bedtime and waking.
- **Relative hypoglycemia:** An event during which typical symptoms of hypoglycemia occur, that does not require the assistance of another person and is accompanied by BG >70 mg/dL (3.9 mmol/L).
- **Probable symptomatic hypoglycemia:** Symptoms of hypoglycemia were present, but BG measurement was not reported.
- Overall hypoglycemia: This optional category combines most cases of hypoglycemia (documented hypoglycemia and probable symptomatic hypoglycemia, including severe hypoglycemia). It does not include relative hypoglycemia. Nocturnal and severe hypoglycemia are special cases of documented or probable hypoglycemia. If an event of hypoglycemia falls into multiple subcategories, that event should only be counted once in the category of overall hypoglycemia.

9.4.2. Severe Hypoglycemia

The determination of a hypoglycemic event as an episode of severe hypoglycemia, as defined in Section 9.4.1, is made by the investigator based upon the medical need of the patient to have required assistance and is not predicated on the report of a patient simply having received assistance.

9.4.3. Electrocardiograms

For each patient, ECGs should be performed at Visit 1 according to the study-specific requirements described in the Schedule of Activities (Section 2).

Electrocardiograms will be interpreted by a qualified physician (the investigator or qualified designee) at the site as soon after the time of ECG collection as possible, and ideally while the patient is still present, to determine whether the patient meets entry criteria and for immediate patient management, should any clinically relevant findings be identified.

Electrocardiograms may be obtained at additional times when deemed clinically necessary.

9.4.4. Vital Signs

For each patient, vital sign measurements should be conducted according to the Schedule of Activities (Section 2) including the study specific requirements.

9.4.5. Laboratory Tests

For each patient, laboratory tests detailed in Appendix 2 should be conducted according to the Schedule of Activities (Section 2).

With the exception of laboratory test results that may unblind the study, Lilly or its designee will provide the investigator with the results of laboratory tests analyzed by a central vendor, if a central vendor is used for the clinical trial.

Any clinically significant findings from laboratory tests that result in a diagnosis and that occur after the patient receives the first dose of IP should be reported to Lilly or its designee as an AE via electronic data entry.

9.4.6. Safety Monitoring

Lilly will periodically review evolving aggregate safety data within the study by appropriate methods.

9.4.6.1. Hepatic Safety Monitoring

If a study patient experiences elevated ALT \geq 3X ULN, ALP \geq 2X ULN, or elevated TBL \geq 2X ULN, liver testing (Appendix 4) should be repeated within 3 to 5 days, including ALT, AST, ALP, TBL, direct bilirubin, gamma-glutamyl transferase, and creatine kinase to confirm the abnormality and to determine if it is increasing or decreasing. If the abnormality persists or worsens, clinical and laboratory monitoring should be initiated by the investigator and in consultation with the study medical monitor. Monitoring of ALT, AST, TBL, and ALP should continue until levels normalize or return to approximate baseline levels.

Hepatic Safety Data Collection

Additional safety data should be collected via the CRF if 1 or more of the following conditions occur:

- o elevation of serum ALT to $\geq 5X$ ULN on 2 or more consecutive blood tests
- o elevated serum TBL to \geq 2X ULN (except for cases of known Gilbert's syndrome)
- o elevation of serum ALP to $\geq 2X$ ULN on 2 or more consecutive blood tests
- patient discontinued from treatment due to a hepatic event or abnormality of liver tests
- o hepatic event considered to be an SAE.

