Study Procedure	Study Screening		Lead-In Period						In	itensi	ve Ti	tratio	n Per	iod		ainten Perio		Safety Follow-Up	ED	
												Tre	atme	nt Per	iod					
eCRF Visit Number	1	2	3a	4a	5	6a	7	8	9a	10	11	12a	13	14a	15	16	17	18	801	EDp
Visit Window (± days)		3	3	3	3	3	3	4	3	3	7	7	7	7	7	7	7	7	7	
Time on Study Relative to First Active	-9	-8	-7	-6	-4	-2	-1	0	1	2	4	6	8	10	12	18	22	26	30	
Treatment Dose (weeks)																				
Ancillary Supplies/Diaries/IP																				
Dispense blood glucose meter and ancillary		X						X		X	X		X		X	X	X	X		
supplies and complete trainingl,m								 												
Dispense study diary		X			X		X	X		X	X		X		X	X	X	X		
Diary use training ^m		X																		
Collect Study Diary and Transfer Diary Data to eCRF (InForm) ⁿ					X		X	X		X	X		X		X	X	X	X	X	X
Train on collecting 4- and 10-point SMBG profiles ^m		X																		
Review 4-point SMBG profiles ^o			X	X	X	X	X	X	X	X	X	X	X	X	X	X	X	X	X	X
Remind patient of 10-point SMBG requirementsp						X	X							X			X			
Review 10-point SMBG profiles								X							X			X		Χq
Review/discuss hypo data			X	X	X	X	X	X	X	X	X	X	X	X	X	X	X	X		X
Dispense IP		X			X			X			X		X		X	X	X			
Patient returns used and unused study drug supplies					X			X			X		X		X	X	X	X		X
Drug accountability					X			X			X		X		X	X	X	X		X
Laboratory Assessments													•					1	1	.1
Patient fasts prior to visit		X						X										X		X
MMTT ^r								X										X		
Urinalysis panel	X																			
Pregnancy test ^S	X							X												
Follicle-stimulating hormone test ^t	X																			
Chemistry panel	X							X										X		X
Fasting serum glucose		X																		
Hematology	X							X										X		X

Study Procedure	Study Screening	Lead-In Period					Intensive Titration Period									intena Period		Safety Follow-Up	ED	
												Trea	tme	nt Per	iod					
eCRF Visit Number	1	2	3a	4a	5	6a	7	8	9a	10	11	12a	13	14a	15	16	17	18	801	EDp
Visit Window (± days)		3	3	3	3	3	3	4	3	3	7	7	7	7	7	7	7	7	7	
Time on Study Relative to First Active	-9	-8	-7	-6	-4	-2	-1	0	1	2	4	6	8	10	12	18	22	26	30	
Treatment Dose (weeks)																				
1,5-Anhydroglucitol								X			X				X			X		X
Hemoglobin A1c	X						X	X			X		X		X			X	X	X
Lipid profile								X										X		X
Anti-insulin lispro antibodies		X						X		X	X				X			X	X	X
Health Outcomes Questionnaires ^u																				
EQ-5D-5L		X						X										X		X
ITSQ		X						X										X		X
WPAI-GH		X						X										X		X

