At Visit 8, patients will be randomized to either LY900014 or insulin lispro at mealtime. During the initial 12 weeks after randomization (intensive titration period), prandial insulin dose should be adjusted as necessary in order to meet the target self-monitored blood glucose (SMBG) levels. Basal insulin may be titrated as needed to facilitate optimal prandial dosing or for safety reasons such as hypoglycemia or unacceptable hyperglycemia. Thereafter, during the maintenance period (Weeks 12-26 of treatment), it is expected that adjustments to prandial and basal insulin

doses would be to maintain glycemic control or for safety reasons such as hypoglycemia or unacceptable hyperglycemia.

Figure ITSD.1 illustrates the study design.

Abbreviation: T = telephone visit.

- At Visit 2, patients on insulin glulisine, insulin aspart, regular human insulin, or premixed insulin will be transferred to insulin lispro. The patients' basal insulin regimen will be switched to insulin glargine U-100 once daily or to insulin degludec U-100 once daily. At Visit 8, patients will be randomized to either premeal insulin lispro or premeal LY900014 and continue their basal insulin regimen.
- b Titrate basal insulin (see Section 7.2.1.3).
- c Titrate prandial insulin (insulin lispro or LY900014) (see Section 7.2.1.4).
- d Patients will discontinue study insulins at Week 26.

Figure ITSD.1. Illustration of study design for Clinical Protocol I8B-FH-ITSD.

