6.2. Exclusion Criteria

Patients will be excluded from study enrollment if they meet any of the following criteria at screening:

Medical Conditions

- [14] Have any other condition (including known drug or alcohol abuse, or psychiatric disorder including eating disorder) that precludes the patient from following and completing the protocol
- [15] Have hypoglycemia unawareness, as judged by the investigator
- [16] Have had more than 1 episode of severe hypoglycemia (defined as requiring assistance due to neurologically disabling hypoglycemia) within the last 6 months prior to screening
- [17] Have had more than 1 emergency room visit or hospitalization due to poor glucose control (hyperglycemia or diabetic ketoacidosis) within 6 months prior to screening (Visit 1)
- [18] Have clinically significant cardiovascular disease within the last 6 months prior to screening, defined as stroke, decompensated heart failure New York Heart Association class III or IV (Appendix 6), myocardial infarction, unstable angina pectoris, or coronary arterial bypass graft

[19] Renal:

- History of renal transplantation
- o Currently receiving renal dialysis
- o Serum creatinine >2.0 mg/dL (177 μmol/L) at screening
- [20] Hepatic: Have obvious clinical signs or symptoms of liver disease (for example, acute or chronic hepatitis, or cirrhosis) or elevated liver enzyme measurements as indicated below at screening (Visit 1):
 - Total bilirubin level (TBL) \ge 2X the upper limit of normal (ULN) (with the exception of Gilbert's syndrome) as defined by the central laboratory,

OR

 Alanine aminotransferase (ALT) ≥3X ULN as defined by the central laboratory

OR

- Aspartate aminotransferase (AST) ≥3X ULN as defined by the central laboratory
- [21] Malignancy: Have active or untreated malignancy, have been in remission from clinically significant malignancy (other than basal cell or squamous cell skin cancer) for less than 5 years, or are at an increased risk for developing cancer or a recurrence of cancer, in the opinion of the investigator
- [22] Have any hypersensitivity or allergy to any of the insulins or excipients used in this trial
- [23] Have hypersensitivity or allergy to any of the ingredients in the standardized test meal (MMTT) (for example, nut allergy)

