8.1.1. Permanent Discontinuation from Study Treatment

Patients will be discontinued from the IP in the following circumstances:

- The investigator may decide that the patient should stop IP. If this decision is made because of an AE, SAE, or a clinically significant laboratory value, the study drug is discontinued for that patient and appropriate measures are to be taken. Lilly or its designee is to be alerted.
- The patient requests to discontinue IP.
- If the patient becomes pregnant.
- If an investigator, study site personnel performing assessments, or patient is unblinded, the patient must discontinue IP.
- If the patient, for any reason, requires treatment with another therapeutic regimen or therapeutic agent that has been demonstrated to be effective for treatment of the study indication. Discontinuation from IP should occur prior to introduction of the new agent.
- Use of prohibited concomitant medication (see Table ITSD.8).
- If the patient has not taken IP for more than 14 consecutive days.
- **Discontinuation due to a hepatic event or liver test abnormality.** Patients who are discontinued from investigational product due to a hepatic event or liver test abnormality should have additional hepatic safety data collected via CRF.

Discontinuation of the investigational product for abnormal liver tests **should be** considered by the investigator when a patient meets one of the following conditions after consultation with the Lilly designated medical monitor:

- alanine aminotransferase (ALT) or aspartate aminotransferase (AST) >8X upper limit of normal (ULN)
- ALT or AST >5X ULN for more than 2 weeks
- ALT or AST >3X ULN and total bilirubin level (TBL) >2X ULN or international normalized ratio (INR) >1.5
- ALT or AST >3X ULN with the appearance of fatigue, nausea, vomiting, right upper-quadrant pain or tenderness, fever, rash, and/or eosinophilia (>5%)
- alkaline phosphatase (ALP) >3X ULN
- ALP >2.5X ULN and TBL >2X ULN
- ALP >2.5X ULN with the appearance of fatigue, nausea, vomiting, right quadrant pain or tenderness, fever, rash, and/or eosinophilia (>5%)

Patients discontinuing from the investigational product prematurely for any reason should complete adverse event and other follow-up procedures per Section 2 (Schedule of Activities), Section 9.2 (Adverse Events), and Section 9.4 (Safety) of this protocol.

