#### 6.12.4.4.3. Treatment-Emergent Elevation of Liver Enzyme Lab Values

The percentages of patients with the following elevations in hepatic laboratory tests at any time during the treatment period (0 to 26) will be summarized between treatment groups:

- The percentages of patients with postbaseline ALT measurement ≥3 times (3X), 5 times (5X), and 10 times (10X) the Covance upper limit of normal (ULN) will be summarized for all patients with a postbaseline value by the following baseline categories: ≤1X, >1X to <3X, ≥3X, missing.
- The percentages of patients with postbaseline AST measurement ≥3 times (3X), 5 times (5X), and 10 times (10X) the Covance ULN will be summarized for all patients with a postbaseline value by the following baseline categories: ≤1X, >1X to <3X, ≥3X, missing.
- The percentages of patients with postbaseline total bilirubin measurement ≥2 times (2X) the Covance ULN will be summarized for all patients with a postbaseline value by the following baseline categories: ≤1X, >1X to <2X, ≥2X, missing.

Baseline will be the maximum observation in the baseline period including the lead-in period. The maximum value will be the maximum value from the treatment period. Planned and unplanned tests will be included.

Graphical profiles of ALT, AST, total bilirubin, and ALP will be provided for patients with an ALT or AST  $\geq$ 3X ULN or total bilirubin  $\geq$ 2X ULN during the treatment period. A listing for these patients will also be provided, including the actual measurement of ALT, AST, ALP, and total bilirubin, the corresponding reference high limits, demographics, disposition, drug exposure and AEs. The review for these patients includes an assessment of the proximity of any ALT or AST elevation to any total bilirubin elevation, ALP levels, other potential causes, and the temporal association with events such as nausea, vomiting, anorexia, abdominal pain, or fatigue.

All patient data, regardless of whether on IP, will be used for the above analyses related to hepatobiliary events.

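### Protocol 9.4.6.1 sets no AST trigger for repeat liver testing or for the laboratory-based CRF collection, although the entry criteria, stopping conditions and SAP treat AST like ALT (low severity)

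*Protocol*

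**What the plan says.** **Hepatic monitoring (Protocol 9.4.6.1).** The rule opens "If a study patient experiences elevated ALT" and names three triggers: ALT ≥3X, ALP ≥2X and TBL ≥2X ULN. Any of them calls for a repeat liver panel in 3 to 5 days. If the abnormality persists or worsens, "clinical and laboratory monitoring should be initiated by the investigator and in consultation with the study medical monitor", and this continues until values are normal or near baseline. AST is measured in the repeat panel and in the later monitoring, but it does not start either.

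**Extra CRF data (same section).** The only aminotransferase trigger begins "elevation of serum ALT to" and requires ≥5X ULN on at least two consecutive tests. The other laboratory triggers are TBL and ALP. Two further triggers are not laboratory values: stopping treatment for a liver reason, and a hepatic SAE.

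**AST elsewhere.** Exclusion 20 lists "Aspartate aminotransferase (AST) ≥3X ULN as defined by the central laboratory" beside the identical ALT limit. Protocol 8.1.1 pairs the two enzymes in all four aminotransferase conditions, for example "ALT or AST >5X ULN for more than 2 weeks". SAP 6.12.4.4.3 tabulates both at 3X, 5X and 10X ULN and adds: "Graphical profiles of ALT, AST, total bilirubin, and ALP will be provided for patients with an ALT or AST" of at least 3X ULN.

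**When liver tests are drawn.** In the Schedule of Activities, the row "Chemistry panel" is marked at Visits 1, 8, 18 and ED. It is blank from Visit 9 to Visit 17 and at Visit 801.

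**The concern.** The entry limits, the conditions for considering discontinuation and the planned tables and listings all treat AST and ALT alike. The section that tells sites when to confirm an abnormal result does not, and no reason is given. A patient can therefore meet the SAP's criterion for an individual profile on AST alone without the protocol ever asking for a second sample.

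This is a matter of patient follow-up and of how interpretable the hepatic listing will be. A single raised AST value, with no confirmation and no trend, gives limited support to the case review that the SAP describes. The primary and multiplicity-adjusted analyses are not involved.

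**Working it through.** No arithmetic applies. The check sets the aminotransferase limits (multiples of ULN) side by side.

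| Place | ALT | AST |
|---|---|---|
| Protocol 6.2, exclusion 20 | ≥3X | ≥3X |
| Protocol 8.1.1 | >8X | same |
| Protocol 8.1.1 | >5X for over 2 weeks | same |
| Protocol 8.1.1 | >3X with TBL >2X or INR >1.5 | same |
| Protocol 8.1.1 | >3X with symptoms, fever, rash or eosinophilia | same |
| SAP 6.12.4.4.3, summaries | ≥3X, 5X, 10X | same |
| SAP 6.12.4.4.3, profiles and listing | ≥3X | same |
| Protocol 9.4.6.1, repeat in 3 to 5 days | ≥3X | none |
| Protocol 9.4.6.1, laboratory CRF trigger | ≥5X on 2 or more consecutive tests | none |

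Of the places compared, 9.4.6.1 is the only one where the two enzymes part.

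**Which results fall through.** An AST rise with ALT ≥3X, ALP ≥2X or TBL ≥2X is already caught. What remains is AST ≥3X with ALT <3X, ALP <2X and TBL <2X. Within that group, AST above 8X, or above 3X with symptoms, brings 8.1.1 into play while the patient is on study insulin. The least-covered case is thus an asymptomatic AST of 3X to 8X.

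**When it would be seen.**
- Visit 1: AST ≥3X is an exclusion, so the question does not arise.
- Visit 8: the sample precedes the first dose of randomised insulin. An isolated rise here is a baseline finding in a patient who screened below 3X.
- Visit 18: the only scheduled post-dose chemistry for a completer. The design figure notes state "Patients will discontinue study insulins at Week 26", so the stopping conditions have little left to act on, and Visit 801 has no chemistry. With ALT 4X, a repeat is due in 3 to 5 days. With AST 4X and ALT 2X, nothing further is scheduled or triggered.
- ED and unscheduled samples: the same difference applies.

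**What else might direct a repeat.**
- Section 9.2 requires documented review of each laboratory safety report, but no repeat follows from that. Its follow-up duty covers AEs that are serious or medically important, judged related, or the cause of stopping; an asymptomatic AST value need not be any of these.
- Section 9.4.5 requires AE reporting of a clinically significant laboratory finding only where it leads to a diagnosis.
- Appendix 4 makes further tests possible, and in some cases required in consultation with the sponsor's physician, but sets no automatic repeat.
- The two non-laboratory CRF triggers need a liver-related discontinuation or a hepatic SAE first.

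None of these directs a repeat for an isolated AST rise.

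**The case against.** The best defence is that triggering on ALT may be deliberate. AST can rise from muscle, and a rule that triggers on ALT, ALP and TBL and then measures AST in the repeat panel is coherent. The hepatic lists also differ in other ways: ALP triggers a repeat in 9.4.6.1 but is absent from exclusion 20 and from the SAP's elevation categories, and its limit in 8.1.1 is not the one in 9.4.6.1. This stands in part. The documents do not exclude intent, and they follow no rule that every analyte appears in every list. But differences in ALP do not explain why ALT and AST, paired in every other place compared, are separated here.

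It is also fair that investigators review every laboratory report, may stop study insulin for a clinically significant value, and may repeat a test at any time. The sponsor also reviews aggregate safety data. These reduce the consequence without supplying the missing instruction.

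Three stronger readings are tempting, and the documents do not support them:
- *That the over-2-weeks condition in 8.1.1 works for ALT and fails for AST.* After the first repeat, 9.4.6.1 fixes no further interval for either enzyme, so the ALT pathway does not secure that check either.
- *That a patient with raised AST at Visit 8 waits until Week 26 for another test.* The next scheduled chemistry is equally distant for ALT, and a discretionary repeat is open throughout. A scheduled visit should not be compared with a triggered repeat as if the difference were the expected delay.
- *That the ALT repeat is mandatory.* The section says testing should be repeated. The difference is between protocol-directed and not directed.

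**Conclusion.** The point holds at low severity. Protocol 9.4.6.1 leaves an isolated AST rise without a directed repeat, without directed monitoring to normal and without a laboratory trigger for extra CRF data, whereas the same ALT rise has them. The practical weight falls mainly on Visit 18, with ED, unscheduled and pre-dose Visit 8 results as lesser cases.

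The documents give no rate of isolated AST elevation, so the number of patients cannot be computed; that it is small is an assumption. The conclusion also assumes that no site instruction outside these documents adds an AST trigger. The omission itself is certain from the text. Whether it is an oversight or a choice is not, and if it was a choice, one sentence of rationale would settle the matter.

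**What to change.** In Protocol 9.4.6.1, make two edits:
- Change the aminotransferase re-test trigger to **ALT or AST ≥3X ULN**, leaving ALP and TBL as they are.
- Change the first CRF trigger to **ALT or AST ≥5X ULN**, keeping its requirement of two or more consecutive tests.

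The sponsor's medical team should confirm the limits or, if ALT-led triggering was intended, state why. Section 8.1.1, the Schedule of Activities and the SAP need no change.

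The cost is two wording edits at the next amendment and the matching CRF instruction. AST is already in routine chemistry (Appendix 2) and in the repeat panel, so no assay is added. The downside is an occasional repeat sample for an AST rise of non-hepatic origin, which the creatine kinase already in the repeat panel helps to identify. The edits give AST the same confirm-and-monitor pathway as ALT; they do not by themselves secure the 2-week check in 8.1.1 for either enzyme.
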